3.1. Study Design Overview

This is a pilot study aiming to assess the feasibility of using a jet injector in the place of a lancet when retrieving a capillary blood sample. Each participant in the study will receive four interventions: the current best practice for capillary blood sampling (a lancet prick), a jet injection with a standard circular orifice, and two jet injections with different custom slot orifices. This study is designed to be single-blinded and all participants will serve as their own control as each participant will receive the lancet based sampling. Participants will be aware they are receiving one of each intervention, but will be blinded to the order and identity of which intervention is occurring at which site. The study will be conducted in the ground floor laboratory space (G20) of the Auckland Bioengineering Institute ([name]).

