3.2. Population & Recruitment

We intend to recruit up to 35 healthy participants to take part in this study. These participants will be divided into two groups with up to 25 participants in the first group and up to 10 in the second. The difference between these groups relates to the measurements that will be made on their blood samples, and also in the injectate used to obtain these measurements. The samples gathered from participants in the first group, using isotonic saline for the jet injections, will be tested for glucose concentration, while those from the second group, using isotonic saline with ICG for the jet injections, will have a fluorescent based dilution measurement. Participants will be aware that the study is structured in this way, and will be aware of which group they are being recruited into.

With a minimum sample size of 20 in the first group we predict we will be able to distinguish statistically significant differences between groups whose mean dilution differs by as little as 10% ($\sigma_{glucometer}$ =0.6 mmol/L, α =0.05, β =0.1). We predict we will be able to observe differences in mean dilution as low as 5% in group 2 with a sample size of at least 8 ($\sigma_{fluorimeter}$ =3%, α =0.05, β =0.1). Sample volume is measured identically across both groups and we predict we will be able to observe differences in mean volume released as low as 0.84 µL ($\sigma_{BloodVolume}$ =1 µL, α =0.05, β =0.1).

The study will be advertised within the Auckland Bioengineering Institute and Department of Engineering Science. This will involve flyers posted within Auckland Bioengineering House ([name]) and an email sent to the Auckland Bioengineering Institute. These advertising materials will recommend that anybody interested in participating get in contact with the researchers for more information. In response to expressions of interest the researchers will provide a copy of the participant information sheet (PIS) and consent form (CF) to give detailed information about the study. Participants will be asked to take their time reading these forms and, if they are interested in participating, to indicate times that might suit them to come in for the study. This will also allow potential participants adequate opportunity to ask questions and seek external advice regarding participation in the study.

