Participants will be required to visit the Auckland Bioengineering Institute for one 45 minute session where the interventions will take place. The participants will be asked to complete a short questionnaire 24 hours after the interventions, and send a photograph of the fingertips to the researchers.

We will aim for gender and ethnic representation in proportion with the greater New Zealand population. We imagine we will be able to get the required number of participants from within the Auckland Bioengineering Institute and Department of Engineering Science. However, if this proves more difficult than expected we will extend the recruitment to the wider University (UoA) using the same flyers and emails.

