3.4. Interventions

Each participant will be subjected to four interventions: a standard lancet prick, a jet injection with a standard circular orifice, and two jet injections with different custom slot orifices. These interventions will be performed on the side of the fingertip of the middle (3rd finger) and ring finger (4th finger) of either hand. Which finger receives which intervention will be randomised, as will the order of the interventions. The participants will be blinded by an opaque barrier which will prevent them observing the procedure but allow them to see and communicate with the practitioner. After each intervention has been applied, and the associated blood samples collected, there will be a 2 minute 'break' before performing the next intervention. The participants will be shown the jet injector and lancing device following the procedures. The interventions will be identical for both groups with the exception of the fluorescent dye (ICG, 0.01 mg/L) added to the jet injected fluid for group 2.

Lancet

Capillary blood will be sampled in accordance with the "WHO guidelines on drawing blood" [8]. This will involve a lancet piercing the skin to a depth of 2.3 mm. The collection of the blood into four sequentially-collected samples differs from the WHO guidelines, but is necessary to the study (see section 3.5), and adds no extra risk to the participant.

Jet Injection

A jet injection of less than 50 μ L of sterile isotonic saline will be performed to pierce the skin. The jet will target the same depth in the dermis as the lancet (2.3 mm). Similarly to the lancet, the jet injector based blood sampling will be done as closely as possible to the WHO guidelines. However, the use of a jet injector itself is not currently within these guidelines, as this is novel to this study.

For group 2 ICG will be added to the injected saline to a concentration of (10 mg/L). An ICG concentration of 10 mg/L is well below the dose used for other diagnostic procedures (5 g/L) approved by the FDA.

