3.7. Materials

Lancet

The lancing will be performed using a standard, commercially available tool (Accu-Check, Safe-T-Pro-Plus). This will be set to penetrate to a depth of 2.3 mm. This device shields the lancet following penetration, making accidental stick injury extremely unlikely.

Jet Injector

The injection system has been designed in accordance with medical electrical equipment safety standard IEC 60601-1. The jet injector includes an electric motor which is momentarily (<0.1 s) supplied with a voltage (<320 V) to perform the injection. All elements of the injector that are exposed to the user are made from plastic and as such, in the very unlikely event of a short circuit within the injector, it is not possible for the participant or researcher to be exposed to the driving voltage. It would require a minimum of three simultaneous faults to expose a participant or researcher to any electrical current. During use all external surfaces of the device remain well below the maximum temperature (40 $^{\circ}$ C) dictated by the IEC 60601-1 standard.

The orifices and ampoules used with the injector must be sterile as they will be in contact with the participant and the injectable fluid. The ampoules with the standard circular orifices come in sterile packaging and will be single use. The custom slot orifices and ampoules are made at the Auckland Bioengineering Institute and will be reused through the trial. This equipment will be cleaned according to AS/NZS 4187:2014, and sterilised using a class B autoclave following use on a participant (and prior to the first use). Similarly to standard medical syringes, a small amount of medical grade silicone lubricant will be used to lubricate the interior of the ampoules.

Injectate

The jet injections will be performed using a volume of less than 50 μ L of sterile isotonic saline. For group 2 this will include ICG at concentration of 10 mg/L. ICG is an FDA approved, fluorescent marker which is commonly used at a concentration of 5 g/L. We will deliver ICG at a concentration five hundred times smaller than this. The ICG solution will be used as a marker that will allow us to measure the dilution of blood samples.

Blood collection/containment

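### Recruiting from the host institute, with no exclusion for team members or people who know the injector, leaves the participant-blinded pain comparison exposed to avoidable bias

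*Protocol*

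**What the plan says.** **Recruitment (Protocol 3.2).** "The study will be advertised within the Auckland Bioengineering Institute and Department of Engineering Science". The team expects this to be enough: "We imagine we will be able to get the required number of participants from within the Auckland Bioengineering Institute and Department of Engineering Science". The wider University is held in reserve, to be approached with the existing flyers and emails only if recruitment proves hard.

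**Link to the device (Protocol 3.1, 3.7).** The study is run in the institute's own laboratory. Section 3.7 adds: "The custom slot orifices and ampoules are made at the Auckland Bioengineering Institute and will be reused through the trial".

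**Eligibility (Protocol 3.3).** There are five exclusions: insulin-dependent diabetes, bleeding or clotting disorders, blood-borne infection, fingertip amputation, and reduced peripheral circulation. None concerns membership of the research team or experience with the injector.

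**Blinding (Protocol 3.1, 3.4).** Participants know they will receive one of each intervention but "will be blinded to the order and identity of which intervention is occurring at which site". The method is given as: "The participants will be blinded by an opaque barrier which will prevent them observing the procedure but allow them to see and communicate with the" member of staff. Then: "The participants will be shown the jet injector and lancing device following the procedures".

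**Outcome (Protocol 2.1 and 3.6).** Question (d) asks whether discomfort with the jet is comparable to, or below, that with a lancet. The evidence is a spoken 0-10 pain score after each intervention and a self-completed questionnaire at 24 hours.

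**The concern.** Pain is the participant's own judgement, so a comparison of jet with lancet depends on the participant not knowing which is which, or at least having no reason to care. Holding back the devices until afterwards suggests that the blind relies partly on participants not already knowing them. Recruiting first from the institute that makes part of the equipment and hosts the study weakens that reliance, and nothing in the eligibility criteria restores it.

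As written, a person who has operated the injector, or who is supervised by an investigator, may enrol and score it. If such people recognise the jet and score it differently for that reason, the jet-lancet difference is biased. Each participant acting as their own control does not remove this, because the shift would apply to one intervention and not the other. Section 3.9 also uses an average pain score as a safety signal, so any shift would carry over there.

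**Working it through.** The protocol gives no standard deviation, detectable difference or sample size for pain, so there is no stated figure to reproduce. The check is a reading of the sections against each other.

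1. **Can an insider enrol?** Yes. Sections 3.2 and 3.3 together place institute members in the first recruitment pool and exclude none of them for knowing the device or working with the team.
2. **Does the masking cover more than sight?** Not as described. Section 3.4 mentions only the barrier. Section 3.7 says: "The jet injector includes an electric motor which is momentarily (<0.1 s) supplied with a voltage (<320 V) to perform the injection". That sentence concerns electrical safety. It shows that the device is motor-driven, but the protocol does not say how it sounds or feels beside the lancing device. A non-visual cue is therefore possible but not documented.
3. **Which outcomes are exposed?** Both pain assessments and the reported skin symptoms are self-reports. The 24-hour pain rating does not rescue the comparison, since it comes from the same person after the devices have been shown. Volume is read from the filled length of a capillary tube, glucose from a glucometer and dilution from a fluorimeter, so a participant's attitude to the device is unlikely to move them.
4. **Which contrast is exposed?** Mainly jet versus lancet. Telling the three orifices apart by feel is less plausible.
5. **How large could the effect be?** Let *f* be the share of participants who recognise the jet and *s* the average shift this causes in their jet-minus-lancet score. Then

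   bias in the mean difference = *f* × *s*.

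   The protocol supplies neither input. Purely as assumptions:
   - *f* = 0.20, *s* = 0.5 points: 0.20 × 0.5 = 0.10 points
   - *f* = 0.50, *s* = 1.5 points: 0.50 × 1.5 = 0.75 points

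   The sign of *s* is unknown, so these assumptions span −0.75 to +0.75 points on the 0-10 scale. The bias is zero if nobody recognises the device or recognition does not alter scoring. These figures show how the bias scales; they do not estimate it.

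**The case against.** The strongest reply is that this is a pilot whose principal question is whether a usable blood sample can be obtained. Discomfort is one of five sub-questions, convenience recruitment is stated openly, and a wider route is already provided. No figure in the protocol is wrong on this point and no passages contradict each other. That is fair, and it limits the weight of the point. It does not remove it, because the protocol claims a participant blind and poses a comparative discomfort question.

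A reader might also infer more than the text supports:

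- **That the blind fails.** Nothing shows that any participant would know or recognise the device, or how many institute members have met it. The blind is at risk and unprotected; it is not shown to be broken.
- **That the institute builds the injector.** The protocol says this of the slot orifices and ampoules (and of the fluorimeter), not of the injector body.
- **That the bias favours the jet.** A colleague may want the device to succeed, but that is a guess at motive. The direction is not established.
- **That excluding insiders secures the blind.** If sound or feel gives the jet away, it may do so for anyone. Every participant knows the set holds one lancet prick and three jet injections, so a naive participant might pick out the odd one.

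The last item is the best criticism of the remedy. The exclusion deals with prior knowledge and personal stake, not with every cue.

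**Conclusion.** The point holds as a gap in safeguards. Recruitment is directed first at the institute that hosts the study and makes the slot orifices and ampoules, no criterion excludes team members or people experienced with the injector, and the described blind is visual only. The self-reported pain comparison for question (d) is therefore open to an avoidable bias whose size and direction the protocol cannot settle.

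This assumes that some eligible members of the recruitment pool have met the injector or have an interest in it, which is plausible but not stated. The principal feasibility question and the physically measured outcomes are little affected. Recruitment source, eligibility and masking are protocol content, and a later analysis could not restore a blind once lost. The change is worth making because it is cheap, not because harm has been demonstrated.

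**What to change.** Add one exclusion to section 3.3: members of the research team, people supervised by them, and anyone who has worked on, operated or previously received an injection from the study jet injector. Keep it that narrow; also excluding everyone who has merely seen the device in use could remove people unnecessarily from a small pilot.

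In section 3.2, advertise to the wider University from the start with the existing flyers and emails, instead of holding that route in reserve. This may also help the stated aim of gender and ethnic representation in line with the national population.

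The cost is one line of text and slightly slower recruitment of at most 25 + 10 = 35 people. The change lowers the risk from participants with prior knowledge or a stake. Because it does not fully secure the blind, section 3.1 should not be read as guaranteeing that participants cannot tell jet from lancet.

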3.3. Eligibility Criteria

Inclusion and exclusion criteria will be the same for both groups in this study.

Inclusion Criteria

- Aged >20 and <60 years old. (Human skin thickness is relatively constant for people between 20 and 60 years, and is reduced outside of this range [7])
- Able to communicate in English
- Able to give full informed consent (i.e. no neurological impairment)

Exclusion Criteria

- Insulin-dependent diabetes. (Due to regular finger-prick testing, these individuals may have scarring of their fingertips, which may influence blood release.)
- Haemophilia (or other bleeding/clotting disorders)
- Carrier of blood-borne infectious agent (e.g. HIV, HBV)
- Amputation affecting a number of fingertips
- Significant peripheral circulatory reduction (e.g. Raynauds disease or beta blocker use)

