While blood extraction with a jet injector has not yet been trialled, one study investigated the ability of a jet injector to extract interstitial fluid [4]. This study attempted to collect the fluid back through the same small orifice through which the jet was formed, and waited less than 0.5 seconds between breaking the skin and collecting the fluid. The volume of fluid collected ranged between 10 μ L and 40 μ L but was found to be mainly derived from the fluid that was injected, with interstitial fluid making up between 1% and 3%. As demonstrated by this study, we anticipate that one of the major problems with obtaining a capillary blood sample using jet injected fluid. As part of this study we wish to investigate the extent of this dilution issue. We propose to measure the dilution by marking our injected fluid with indocyanine green (ICG), an FDA approved fluorescent marker. By exciting the retrieved blood samples with 780 nm light, and measuring the resulting fluorescence we will be able to measure the dilution of the sample.

ICG is commonly used for diagnostic purposes (e.g., cardiocirculatory, retinal and liver function diagnostic tests), typically at a dose of no more than 2 mg/kg and a concentration of 5 g/L [5]. ICG has been delivered transdermally into the subcutaneous tissue in multiple fluorescent lymphography studies, and into the dermal layer in a recent study performing fluorescent microscopy. Delivery of 20 μ L of 5 g/L ICG into the dermis was described as having a "short-time tolerable burning sensation" [6], but in this study we plan to use a concentration of only 10 mg/L.

2. Research Aims

In this study we intend to use needle-free jet injection not to deliver a drug, but instead just to pierce the skin with a small volume of isotonic saline or ICG solution, and then retrieve a capillary blood sample. Ultimately we believe a single jet injection device may be able to extract blood, perform a blood glucose measurement and then, based on this measurement, deliver the ideal volume of insulin. However, this study will focus only on establishing the ability of this technique to achieve a measurement of blood glucose concentration.

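### Section 3.3 has no exclusion for known allergy or hypersensitivity to indocyanine green (ICG), which Group 2 receives in three jet injections

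*Protocol*

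**What the plan says.** Protocol section 3.3 opens with "Inclusion and exclusion criteria will be the same for both groups in this study". It then lists five exclusions: insulin-dependent diabetes (because of fingertip scarring), haemophilia or another bleeding or clotting disorder, carriage of a blood-borne infectious agent, amputation affecting fingertips, and finally "Significant peripheral circulatory reduction (e.g. Raynauds disease or beta blocker use".

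The groups differ in what is injected. Section 3.2 describes the samples of Group 1 as obtained with plain isotonic saline, and "those from the second group, using isotonic saline with ICG for the jet injections". Section 3.4 gives every participant a lancet prick, "a jet injection with a standard circular orifice, and two jet injections with different custom slot orifices", which makes three jet injections each. It also states "For group 2 ICG will be added to the injected saline to a concentration of (10 mg/L"), and section 3.7 repeats the concentration: "For group 2 this will include ICG at concentration of 10 mg/L".

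On tolerability, section 1 cites one study of ICG in the dermis at 5 g/L, described as causing a "short-time tolerable burning sensation". Allergy and hypersensitivity are mentioned nowhere in the protocol.

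**The concern.** The five exclusions deal with the fingertip, bleeding, circulation and infection. They suit a study of skin puncture and blood release. None deals with the substance being injected, although Group 2 is the part of the study in which a dye is put into the skin of healthy volunteers.

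The general rule is that a person known to react to an agent is not given it. As section 3.3 stands, staff who follow it exactly would accept such a person into Group 2. The fault is the missing criterion. Using one list for both groups is not itself wrong, since a common list could carry the exclusion.

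What is at stake is the safety of a rare individual. Exposing a volunteer already known to react can be avoided and brings no scientific benefit, because the same person could take part in Group 1. The validity of the results is not in question.

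**Working it through.** No figure in the protocol is disputed. The check has two parts: whether any criterion covers ICG, and how large the exposure is.

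**Coverage by the criteria**

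| Exclusion in 3.3 | Concerns the injected agent? |
|---|---|
| Insulin-dependent diabetes | No |
| Bleeding or clotting disorder | No |
| Blood-borne infectious agent | No |
| Fingertip amputation | No |
| Reduced peripheral circulation | No |

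The three inclusion criteria (age, English, capacity to consent) do not cover it either. Section 3.6 collects pain and site reactions after each intervention and again at 24 hours, and section 3.9 sets up a committee that meets every fortnight. Both act after exposure. Section 3.9 names pain, bruising, excessive bleeding, infection and nerve damage, but not allergic reaction.

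**Inputs for exposure**
- ICG concentration: 10 mg/L (sections 1, 3.4 and 3.7). Section 3.4 also prints 0.01 mg/L, so both are carried through.
- Volume: under 50 μL per injection (sections 3.4 and 3.7).
- Jet injections per participant: 3 (section 3.4).
- Group 2 size: at least 8, at most 10 (section 3.2).
- Comparators in section 1: 20 μL at 5 g/L in the dermis, and no more than 2 mg/kg in diagnostic use.

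**The protocol's own figure.** Section 3.7 says the concentration is five hundred times smaller than usual: 5,000 mg/L ÷ 10 mg/L = 500. This reproduces.

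**Number of ICG injections.** 8 × 3 = 24 to 10 × 3 = 30.

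**Dose = volume × concentration**
- At 10 mg/L: under 50 μL × 10 mg/L = under 0.5 μg per injection, and × 3 = under 1.5 μg per participant.
- At 0.01 mg/L: under 0.5 ng per injection and under 1.5 ng per participant.

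**Against the comparators (at 10 mg/L)**
- Cited dermal dose: 20 μL × 5 g/L = 100 μg. Then 100 ÷ 0.5 = 200 per injection, and 100 ÷ 1.5 = 66.7, about 67, per participant. Because the planned volume is below 50 μL, the true ratios are larger.
- Diagnostic dose at an assumed body weight of 50 to 100 kg: 2 mg/kg gives 100 to 200 mg. Divided by 1.5 μg, that is about 67,000 to 133,000.

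**Chance that Group 2 includes at least one known reactor.** The protocol gives no prevalence p, so two values are assumed. The formula is 1 − (1 − p)^n.

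| Assumed p | n = 8 | n = 10 |
|---|---|---|
| 1 in 1,000 | 1 − 0.999^8 = 0.797% | 1 − 0.999^10 = 0.996% |
| 1 in 100,000 | 0.0080% | 0.0100% |

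These values also assume that nobody who knows of a reaction declines to take part, so for a given p they overstate the chance of exposure.

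**The case against.** The strongest reply is that no sentence in section 3.3 is false or contradictory, and that this is a suggested addition with no documented hazard behind it. The protocol reports only a brief burning sensation, at 500 times the planned concentration, and describes ICG as approved and commonly used. An allergy line could be proposed for almost any protocol that injects something.

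Volunteers are also informed. Section 3.2 says they know which group they are joining and receive an information sheet and consent form, and adds "This will also allow potential participants adequate opportunity to ask questions and seek external advice regarding participation in the study". Section 3.8 provides clinical oversight and a healthcare professional for the sampling. A criterion limited to known reactions concerns people who would probably identify themselves. The consent material, which was not available, may already ask. Finally, the probabilities come from assumed prevalences and span two orders of magnitude only because the assumptions do.

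Much of this stands. The likelihood is very low, the protocol does not show how severe a reaction would be, and the probabilities illustrate scale without being evidence of risk. It cannot be claimed that nothing screens for ICG allergy.

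It does not remove the point. Eligibility is fixed in the protocol and is not normally left to an analysis plan. A list that admits a person known to react to the injected agent is incomplete on its face. Comparisons of dose speak to general tolerability, and the protocol names no dose that is safe for someone already sensitised. Self-withdrawal depends on the volunteer making the connection, whereas a criterion obliges the researchers to ask.

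**Conclusion.** The point holds, as a minor one. Section 3.3 contains no exclusion for known allergy or hypersensitivity to ICG, and as written it admits such a volunteer to Group 2. The claim goes no further than that section, because the information sheet and consent form could not be seen.

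The size is small: 8 to 10 people, 24 to 30 ICG injections and under 1.5 μg per person. The chance that a known reactor is among them depends wholly on the assumed prevalence, and is at most about 1% at the higher value tried. No sample size, power, estimate or conclusion changes. The conclusion rests on the wording of the eligibility list and on the general rule about known reactions. It does not rest on any documented rate of ICG allergy, nor on which of the two concentrations printed in section 3.4 is correct.

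**What to change.** Add to the exclusion criteria in section 3.3: *Group 2 only: known allergy or hypersensitivity to ICG or to any constituent of the ICG product used.* Amend the opening sentence of 3.3 to say that the criteria are common to both groups apart from this one. Ask the question before enrolment, and offer Group 1 to anyone who answers yes. If the consent material already asks, the change simply brings section 3.3 into line with practice.

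The cost is one exclusion line, one amended sentence and one screening question. The only downside is an occasional volunteer moved from Group 2 to Group 1.
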